7.8.4 ECG

Newly emergent abnormalities will be recorded and analysed as AEs if judged clinically relevant by the investigator.

The ECG analyses will be performed using the ECG Set, except those concerning the relationship between plasma concentrations and ECG endpoints which will be based on the ECG-PK set. All analyses will be based on the centrally evaluated ECG data collected until the safety cut-off date of 9th December 2016. Centrally evaluated ECGs recorded after this date, will only be presented in listings.

Descriptive analyses (separate analysis of Phase Ib and Phase II parts)

Absolute values and change from baseline in QTcF interval, QT interval, heart rate, PR interval, and QRS complex will be summarized descriptively by initial treatment, cycle, day and planned time.

Frequency tables will be provided for all categorical endpoints including notable findings and qualitative ECG assessments. Frequencies of the increases in QTcF and QT intervals above thresholds such as 450 msec, 480 msec, and 500 msec between baseline and on-treatment values will be displayed in two-way shift tables by initial treatment.

Notable findings (occurring until the safety cut-off date) of patients in the TS who are excluded from the ECG Set will be listed in separate listings which will be presented in Section 15 of the CTR.

The QTcB interval as well as the percentage changes for PR interval and QRS complex will only be displayed in Listings (Appendix 16.2.8)

Additional statistical analyses will be performed for the Phase II part as described below:

Repeated measures analyses

The endpoint 'change in QTcF interval between baseline and on-treatment' will be analysed by a linear mixed-effects model for repeated measures (MMRM). This model will include the fixed, categorical effects of 'treatment' and 'timepoint', the 'treatment-by- timepoint' interaction, as well as the continuous, fixed covariate 'baseline' and the 'baseline-by- timepoint' interaction. An unstructured covariance structure will be used to model the within-patient measurements. The SAS® procedure MIXED will be used, involving the restricted maximum likelihood estimation method, and the Kenward-Roger method will be applied to adjust standard errors and estimate denominator degrees of freedom. The model is detailed in [Section 9.2.2](#).

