	Both measurements taken before “start of infusion”	Both measurements taken not earlier than 15 min before “end of infusion”
Cycle 1, Day 1	n.a. (Baseline ECG)	Deviation \leq 4 h
Cycle 1, Day 8, 15	Deviation \leq 6 h	Deviation \leq 4 h
Cycles 2 and 3, Day 1		
Cycles >3, Day 1	Deviation \leq 6 h	n.a.
EoT, FU	(no infusion)	Deviation \leq 8 h

For further details see also [Section 6.6.5](#).

The relationship between xentuzumab plasma concentrations and QTcF change from baseline will be explored using a random coefficient model including a categorical variable ‘treatment’ with the two levels ‘xentuzumab+ everolimus+exemestane and ‘everolimus+exemestane’ to estimate the adjusted mean difference between ‘xentuzumab + everolimus+exemestane’ and ‘everolimus+exemestane’ in QTcF change from baseline and its two-sided 90% CI at clinically relevant plasma concentrations, which are the geometric means of the C1D1_{1:15h}, C2D1_{1:15h} and C3D1_{1:15h} values of the RP2D. The model is detailed in [Section 9.2.3](#). For visualization, plasma concentration against QTcF changes from baseline will be plotted, as well as the (fixed effect) regression line, its 90% CI and the geometric means of C1D1_{1:15h}, C2D1_{1:15h} and C3D1_{1:15h}.

The assumption of a linear relationship will be checked by visual inspection of diagnostic plots (presented in Section 16.1.9.2 of the CTR). If linearity is not given, the concentrations may be log-transformed prior to the analysis.

To inspect (graphically) whether the peaks of the time-profiles for xentuzumab plasma concentrations and QTcF interval changes from baseline coincide, figures of the individual time profiles of xentuzumab plasma concentrations and QTcF interval changes from baseline will be generated for each patient (presented in Appendix 16.1.9.2 of the CTR), as well as for the means (presented in Section 15 of the CTR). Mean time profiles from the patients treated with ‘everolimus+exemestane’ alone will be displayed as well.

[figure not shown]
These analyses will also be performed using the corresponding endpoints based on the QT interval and heart rate.

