Furthermore, a first sensitivity analysis will be performed using the random coefficient model described above including the categorical effect ‘day’, and a second sensitivity analysis will be done including the categorical effect ‘time’ with the two levels pre- and post-dose, instead. A further analysis will consider the influence of baseline and will include the centered baseline as a covariate additionally to the factors used in the first sensitivity analysis. These analyses will only be applied to the QTcF changes from baseline.

Proprietary confidential information © 2018 Boehringer Ingelheim International GmbH or one or more of its affiliated companies

Appropriateness of QT interval correction methods for heart rate

To evaluate the appropriateness of the methods, slopes of the relationship of QT, QTcF, and QTcB interval versus RR interval (values log-transformed using the natural logarithm) will be estimated by applying a random coefficient model (see [Section 9.2.4](#)) separately for the treatments ‘xentuzumab+ everolimus+exemestane’ and ‘everolimus+exemestane’. These analyses will be based on the three single on-treatment ECG recordings per time point. A table of the resulting (fixed effect) slopes will be displayed together with two-sided 95% CIs in Appendix 16.1.9.2 of the CTR.

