9.2.3 Description of the random coefficient model used for the exposure-response analyses

The relationship between xentuzumab plasma concentrations and ECG endpoints will be explored using a random coefficient model which includes a categorical effect 'treatment' (with the two levels 'xentuzumab+ everolimus+exemestane' and 'everolimus+exemestane'), 'day' or 'time', respectively, as fixed categorical effects (only used in the sensitivity analyses), as well as a random intercept and slope for each patient ([R17-0553](#), Model Δ QTc3):

$$Y_{ijk} = \tau_j + \zeta_k + a_i + b_i X_{ijk} + \beta X_{ijk} + e_{ijk},$$

$$(a_i, b_i) \sim N_2(\mathbf{0}, \Sigma), e_{ijk} \sim iid N(0, \sigma^2),$$

where

Proprietary confidential information © 2018 Boehringer Ingelheim International GmbH or one or more of its affiliated companies

$i = 1, 2, \dots, I$ indicates the patient (I = total number of patients across all treatment groups, $k = 1, 2, \dots, K_i$ the time point and $j=1,2$ the treatment),

Y_{ijk} is the QTcF change from baseline in patient i receiving treatment j at time point k ,

X_{ijk} is the plasma concentration in patient i receiving treatment j at time point k

τ_j is the effect of treatment j on intercept,

ζ_k is the effect of day (or time, respectively) k on intercept (will only be used in the sensitivity analyses),

a_i is the random effect on intercept associated with patient i ,

β is the overall slope for the relationship between Y_{ik} and X_{ik}

b_i is the random effect on slope associated with patient i ,

e_{ijk} is the random error associated with patient i receiving treatment j at time point k , and

Σ is a 2-by-2 unstructured covariance matrix.

The random error is assumed to be independent of random intercept and slope effects.

The following SAS code will be used to fit the model:

```
PROC MIXED DATA=xxxx METHOD=REML;
CLASS patient treat day1;
MODEL ECGep = conc treat day1/ NOINT CL ALPHA=0.1 ALPHAP=0.1
DDFM=KENWARDROGER;
RANDOM INT conc / TYPE=UN SUBJECT=patient;
ESTIMATE "Pred. value at conc. xx.xx" conc xx.xx treat 1 -1/ CL ALPHA=0.1;
ESTIMATE "Slope estimate" conc 1 / CL ALPHA=0.1;
RUN;
QUIT;
1: class variable 'day' (or 'time', respectively) will only be included in the sensitivity
analyses.
```

Note that the variable names (e.g. 'patient', 'conc' etc.) given in the SAS code above have to be replaced by the respective variable names used in the analysis data set. ECGep corresponds to 'QTcF change from baseline'.

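### Adding baseline QTcF to the main concentration-QTcF model would cost nothing; the SAP plans it only in a further QTcF analysis, and not at all for QT or heart rate

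*SAP*

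**What the plan says.** SAP 7.8.4 (Exposure-response analyses) states that the relation between xentuzumab concentration and "QTcF change from baseline will be explored using a random coefficient model including a categorical variable" for treatment. The target is the adjusted mean difference between arms with "its two-sided 90% CI at clinically relevant plasma concentrations". Control patients enter with concentration zero.

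SAP 9.2.3 gives the equation and the code. The equation has a treatment intercept, a common concentration slope, and a random intercept and slope per patient. The code reads "MODEL ECGep = conc treat day1/ NOINT CL ALPHA=0.1 ALPHAP=0.1", with 'day' or 'time' used only in the sensitivity analyses. The prediction is requested by "conc xx.xx treat 1 -1/ CL ALPHA=0.1". Neither the equation nor the code has a baseline term. The section names a published model form as its source.

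The repeated-measures model (SAP 7.8.4 and 9.2.2) uses the same endpoint. It contains treatment, timepoint and their interaction, "as well as the continuous, fixed covariate" baseline, and a baseline-by-timepoint interaction. It is also run for QT and heart rate.

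The exposure-response model is likewise repeated for QT and heart rate. Its sensitivity analyses are limited to QTcF. The last of them is announced as follows: "A further analysis will consider the influence of baseline and will include the centered baseline as a covariate". The covariate is added to the model that already contains 'day'; SAP 9.2.3 gives no equation or code for this analysis.

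**The concern.** The baseline is one triplicate taken before the first dose (SAP 6.7.1 and 9.2.1), so it carries within-patient variation. Unless baseline and on-treatment values correlate perfectly, change from baseline is negatively related to baseline. An arm that happens to start lower will then show a larger mean change with no drug effect.

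The concentration slope is estimated largely within patients and is little affected. The arm contrast is estimated between patients, and the reported prediction adds the two. Baseline differences between arms therefore enter the predicted difference, and baseline variation widens its interval.

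At stake is the precision of the reported difference and how far it depends on the observed baseline means. The SAP treats baseline as worth adjusting for in one QTcF analysis and gives no reason for leaving it out of the main version of the other.

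**Working it through.** **Inputs.** The documents state no SD, correlation, precision or ECG-PK set size for QTcF, so there is no plan figure to reproduce and every magnitude below is conditional on assumptions.

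- Time points: SAP Table 7.8.4: 1 allows one post-dose value on Cycle 1 Day 1, and pre- and post-dose values on Cycle 1 Days 8 and 15 and on Day 1 of Cycles 2 and 3. That gives 1 + 4 × 2 = 9 on-treatment values through Cycle 3 (m = 9).
- Patients: 70 per arm is assumed. Protocol 3.1 plans about 75, and SAP 4.2 records that recruitment was stopped.
- SDs (assumed, msec): between-patient sb and within-patient sw of (12, 6), (15, 9) and (18, 10).

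**What is estimated.** Predicted difference at concentration x = (slope × x) + (xentuzumab-arm intercept − control-arm intercept). The formulas in step 1 cover the intercept contrast alone.

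**Step 1: closed form with assumed SDs.**

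- Unadjusted patient-level variance: sw² + sw²/m
- Adjusted variance: sb²sw²/(sb² + sw²) + sw²/m
- SE of the contrast: √(2 × variance/70)
- Slope of change on baseline: −sw²/(sb² + sw²)
- SE of the baseline difference: √(2(sb² + sw²)/70)

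For (15, 9), the unadjusted variance is 81 + 9 = 90, so SE = √(180/70) = 1.60. The adjusted variance is 225 × 81/306 + 9 = 68.56, so SE = √(137.12/70) = 1.40. The slope is −81/306 = −0.26 and the baseline-difference SE is √(612/70) = 2.96. A 1-SE imbalance therefore shifts the estimate by 0.78 msec.

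| sb, sw | Implied correlation | SE unadjusted → adjusted | Reduction | Slope | 1-SE imbalance | Shift |
|---|---|---|---|---|---|---|
| 12, 6 | 0.80 | 1.07 → 0.97 | 9% | −0.20 | 2.27 | 0.45 |
| 15, 9 | 0.74 | 1.60 → 1.40 | 13% | −0.26 | 2.96 | 0.78 |
| 18, 10 | 0.76 | 1.78 → 1.58 | 11% | −0.24 | 3.48 | 0.82 |

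In terms of the 90% half-width (1.645 × SE), the gain is about 0.2 to 0.3 msec. For another arm size n, the SEs and shifts scale by √(70/n), for example by 1.18 at n = 50. The percentage reductions do not change.

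**Step 2: dependence on the correlation ρ.** Unadjusted over adjusted CI width is √(2/(1+ρ)) for one on-treatment value. For the mean of m values it is √[(a + 1 − 2ρ)/(a − ρ²)], with a = (1 + (m−1)ρ)/m.

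| ρ | One value | Mean of 9 | Shift from a 5 msec imbalance, −(1−ρ) × 5 |
|---|---|---|---|
| 0.5 | 1.155 | 1.35 | −2.5 |
| 0.7 | 1.085 | 1.17 | −1.5 |
| 0.9 | 1.026 | 1.05 | −0.5 |

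**Step 3: the full model.** The SAP 9.2.3 model, including the concentration term and both random effects, was fitted by REML to simulated trials with and without centred baseline. Assumptions were 70 patients per arm, total SD 18 msec, 9 on-treatment values, no drug effect and assumed relative concentrations.

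| ρ | 90% half-width, unadjusted → adjusted (msec) | Ratio | Slope of estimate on imbalance, unadjusted → adjusted |
|---|---|---|---|
| 0.5 | 3.70 → 2.87 | 1.29 | −0.55 → −0.06 |
| 0.7 | 2.99 → 2.60 | 1.15 | −0.38 → −0.07 |
| 0.85 | 2.10 → 1.99 | 1.05 | −0.23 → −0.09 |

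With 25 simulated trials per ρ, the slopes are imprecise, but the pattern agrees with steps 1 and 2. The summary range of 3-30% takes its lower end from the single-value formula at ρ = 0.9 and its upper end from the full model at ρ = 0.5. The mean-of-9 formula at ρ = 0.5 gives a higher figure, 35%, but it leaves out the concentration term.

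**The case against.** The strongest reply is that the SAP already plans the adjusted analysis for QTcF. Because it is built on the first sensitivity analysis, comparing those two isolates the effect of baseline. The repeated-measures results are also adjusted, so readers will see QTcF with and without baseline. This stands: for QTcF the question is which model leads. It does not reach the QT and heart-rate exposure-response fits, and comparing the main model with the further analysis changes baseline and 'day' together.

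The main model follows a cited published form. That explains where it came from, but the documents give no reason for omitting baseline, and nothing in them requires the omission.

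The analysis is exploratory. Protocol 7.1 plans no formal testing, SAP 7.8.4 says the relationship is to be explored, and no threshold or decision rule is attached to this 90% CI in the available text. This stands and limits the importance of the point. A reader might take the predicted difference to be the trial's headline QT result, but the documents never rank it so.

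The size is assumed and may be small. Baseline averages three ECGs, which raises the correlation, and at 0.85-0.9 the interval is only about 3-5% wider without adjustment. This also stands.

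A reader might also infer that the two QTcF analyses could disagree through baseline alone. They already differ in analysis set, target quantity, time effects and covariance structure, and adding baseline here would remove only one of those differences.

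**Conclusion.** The point holds as a low-cost improvement, not as an error. The main model omits a covariate that the SAP uses elsewhere for the same endpoint. The adjusted version is secondary and combined with 'day' for QTcF, and is absent for QT and heart rate.

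It would be tempting to say that the unadjusted difference is biased. The documents do not support that: allocation is randomised 1:1, so the change-score contrast is unbiased on average, and its CI reflects chance imbalance. What remains is a loss of precision and a shift conditional on the imbalance actually observed. One qualification is that xentuzumab patients enter the ECG-PK set only with a valid time-matched pair (SAP 6.3), a condition control patients do not face, so imbalance in that set need not be purely chance.

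The size is 3-30% in CI width for assumed correlations of 0.9 down to 0.5, and a shift of about 0.5-0.8 msec for a 1-SE imbalance under the assumed SDs and 70 patients per arm. None of these inputs comes from the documents.

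**What to change.** In SAP 7.8.4 and 9.2.3, add centred baseline (patient value minus the overall mean) as a fixed covariate to the main equation and code: `MODEL ECGep = conc treat cbase`. The ESTIMATE statements need no change, because the covariate has coefficient zero in the arm difference. Apply the same term to the QT and heart-rate versions, each with its own baseline. Keep the model without baseline as a sensitivity analysis, so that the effect of baseline can be read directly against the main model.

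The cost is one model term and a sentence of SAP text. No new data are needed and no patient is lost, since a change from baseline already requires a baseline value.

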7.9.6 Immune response (ADA)

Following the changes described in [Section 4.2](#), immunogenicity will be analysed as follows:

The number and percentage of ADA-positive, ADA-negative and ADA-negative-inconclusive patients may be presented. Further analyses related to immunogenicity might be performed if feasible and considered reasonable, e.g. potential impact on PK or PD parameters.

9 ADDITIONAL SECTIONS

9.1 SAFETY ANALYSIS

After 12 evaluable patients treated at the designated MTD dose completed at least the first course of treatment during the phase Ib part, a safety analysis was performed. For this purpose a database snapshot was performed. The safety analysis summarised results regarding safety and was used for recommendation of the dose of trial medication to be taken forward as recommended phase II dose. The selection of the RP2D considered overall safety observed during available treatment cycles for all treated patients, including the ones that were replaced for the determination of the MTD. These analyses were documented in a SIR for the Phase Ib part ([c03569433-01](#)).

Disposition of patients, demographic characteristics and oncological history, previous therapies (listing), concomitant therapies (listing), exposure (total duration of treatment, patients with dose reduction), adverse events and laboratory parameters (listing of laboratory values, table of frequency of patients with transitions of CTCAE grades at baseline and worst grade on treatment) were shown in the safety analysis.

A version of the TSAP was signed before the snapshot of the safety analysis was performed.

9.2 ECG EVALUATION

This section only applies to the centrally evaluated digital ECG recordings.

9.2.1 Derivation of ECG variables

Three replicate digital ECG recordings will be collected at each time point (see also [Section 9.2.5](#)). Each of the three recorded single ECGs will then be evaluated for cardiac intervals, which comprise the RR interval, PR interval, QT interval, and QRS complex. Measurements of these intervals will be made on the three (possibly consecutive) cardiac cycles (also denoted as beats or waveforms) from the lead chosen (usually lead II). The measurements of the cardiac cycles will be stored in the database, i.e., 9 values per time point. All cardiac intervals will be given in milliseconds (msec). The three cardiac cycles will be averaged prior to the calculation of heart rate and heart-rate-corrected QT intervals (QTc).

Heart rate will be derived from the RR interval as

$$\text{Heart Rate [beats/min]} = 60\ 000 / \text{RR [msec]}$$

Two Heart Rate-correction methods of the QT interval will be applied:

- QTcF is the length of the QT interval corrected for heart rate by Fridericia's formula:

$$QTcF[\text{msec}] = \left(\frac{1000}{RR} \right)^{1/3} * QT[\text{msec}]$$

Proprietary confidential information © 2018 Boehringer Ingelheim International GmbH or one or more of its affiliated companies

- QTcB is the length of the QT interval corrected for heart rate by Bazett's formula:

$$QTcB[msec] = \left(\frac{1000}{RR} \right)^{1/2} * QT[msec]$$

Further aggregation of the three replicate QT/QTc intervals and heart rates at each scheduled time point will be performed using arithmetic means. These values will be used for the derivation of the ECG endpoints as they are specified in [Section 5.4.6](#).

9.2.2 Description of the model used for the repeated measures analyses

The model (M1) is described by the following equation

$$Y_{ijk} - B_i = \mu + \tau_j + \zeta_k + (\tau\zeta)_{jk} + (\gamma + \gamma_k)B_i + e_{ik},$$

$$(e_{i1}, \dots, e_{iK}) \sim N_K(0, \Psi)$$

where

$i=1, \dots, I$ indicates the patient, $k=1, \dots, K$ the on-treatment timepoint and $j=1, 2$ the treatment group,

- Y_{ijk} is the QTcF interval measured on patient i receiving treatment j at timepoint k ,
- B_i is the baseline measurement of patient i ,
- μ is the overall intercept,
- τ_j is the fixed, categorical effect of treatment j ,
- ζ_k is the fixed, categorical effect of timepoint k ,
- $(\tau\zeta)_{jk}$ is the interaction effect between treatment j and timepoint k ,
- γ is the fixed coefficient for baseline,
- γ_k is the fixed coefficient for baseline at timepoint k ,
- e_{ik} is the random error associated with patient i at timepoint k ,
- Ψ is a K -by- K covariance matrix of the type 'unstructured'.

The following SAS code (1) will be used to fit the model:

```
PROC MIXED DATA=xxxx ORDER=data CL METHOD=REML;
  CLASS patient treat timepoint;
  MODEL ECGep= treat timepoint treat*timepoint base base*timepoint
  /DDFM=KR;
  REPEATED timepoint / SUBJECT=patient TYPE=UN R RCORR;
  LSMEANS treat*timepoint/ diff CL ALPHA=0.10;
RUN; QUIT;
```

Proprietary confidential information © 2018 Boehringer Ingelheim International GmbH or one or more of its affiliated companies

The variable names (e.g. 'patient', 'treat' etc.) given in the SAS code above have to be replaced by the respective variable names used in the analysis data set. ECGep corresponds to the 'QTcF change from baseline'.

The variable 'timepoint' will be concatenated of 'day' and 'time'. The variable 'day' denotes the consecutive days with ECG recordings (i.e., C1D1, C1D8, C1D15, C2D1, C3D1 etc.) and the variable 'time' will have 2 values (0, 1) indicating whether the ECG was recorded before ('0') or after ('1') drug administration. In terms of SAS code, the interaction 'day*time' corresponds to the effect 'timepoint'.

Therefore, the following SAS code using 'day' and 'time' as separate class variables will be equivalent to the SAS code (1) above:

```
PROC MIXED DATA=xxxx ORDER=data CL METHOD=REML;
  CLASS patient treat day time;
  MODEL ECGep= treat day*time treat*day*time base base*day*time /DDFM=KR;
  REPEATED day*time / SUBJECT=patient TYPE=UN R RCORR;
  LSMEANS treat*day*time/ diff CL ALPHA=0.10;
RUN; QUIT;
```

In case of convergence problems, apply step 1)-6):

- 1) Set SINGULAR=1E-10 as option in the model statement
- 2) Set MAXITER=100 and/or MAXFUNC=200
- 3) Use option SCORING=4 in the final run to request a Fisher scoring algorithm to be used for the first 4 iterations
- 4) Include the additional statement in the PROC MIXED call:
PERFORMANCE NOTHREAD;
- 5) Perform an initial run including the statement
ODS OUTPUT COVPARMS=covstart;

followed by a final run using

```
PARMS / PARMSDATA=covstart;
```

In the special case with the note "Convergence criteria met but final hessian is not positive definite" try instead/in addition

```
PARMS / OLS;
```

to request ordinary least squares starting values.

- 6) One may also use estimates from a simpler model (e.g. using TOEPH) as starting values for the run with TYPE=UN

In case that an unstructured covariance matrix still does not converge, even after application of the above steps, the Toeplitz structure with heterogeneous variances (TOEPH) will be applied.

The statistical model applied as sensitivity analysis will be identical to the model (M1) described above, with the exception of the covariance structure used to model the within-patient measurements.

Proprietary confidential information © 2018 Boehringer Ingelheim International GmbH or one or more of its affiliated companies

The following model (M2) will be used (note that the index k is now replaced by the two indices d and t):

$$Y_{ijdt} - B_i = \mu + \tau_j + \zeta_{dt} + (\tau\zeta)_{jdt} + (\gamma + \gamma_{dt})B_i + s_{it} + e_{idt},$$

$$(s_{i0}, s_{i1}) \sim N_2(0, \Sigma), (e_{id0}, e_{id1}) \sim N_2(0, \Psi)$$

where

- i=1,...,I indicates the patient, d=1,...D the day of ECG recording, t=0, 1 the time of ECG recording (0= before and 1= after drug administration), and j=1, 2 the treatment group,
- s_{it} is the random effect associated with patient i at time t; assumed to be independent across patients,
- e_{idt} is the random error associated with patient i on day d and time t; assumed to be independent across day and patient. The e_{idt} are assumed to be independent of the s_{it} ,
- Σ, Ψ are 2-by-2 covariance matrices of the type 'unstructured'.

The following SAS code will be used to fit this model:

```
PROC MIXED DATA=xxxx ORDER=data CL METHOD=REML;
  CLASS patient treat day time;
  MODEL ECGp= treat day*time treat*day*time base base*day*time /DDFM=KR;
  RANDOM time / SUBJECT=patient TYPE=UN R RCORR;
  REPEATED time / SUBJECT=patient*day TYPE=UN R RCORR;
  LSMEANS treat*day*time/ diff CL ALPHA=0.10;
RUN; QUIT;
```

